7.2. Study Termination Criteria

The study may be terminated at any time by the sponsor for any reason.

Table 3: Schedule of Assessments Enrollment to Week 40

Study Visit Number Study Visit Week (± 3 days)	V 1E	V 2E	V 3E	V 4E	V 5E	V 6E	V 7E	V 8E	V 9E	V 10E	V 11E	V 12E	V 13E
	Day 1	W2	W4	W6	W8	W12	W16	W20	W24	W28	W32	W36	W40
Obtain informed consent/assent	X												
Inclusion/exclusion criteria	X												
Interactive Voice/Web Response System (IXRS) subject registry/visit	X	X	X	X	X	X	X	X	X	X	X	X	X
Dispense study medication	X	X ^a	X	X ^a	X	X	X	X	X	X	X	X	X
Study drug accountability/assess compliance		X	X	X	X	X	X	X	X	X	X	X	X
Clinical and Laboratory Evaluations: ALL SUBJECTS													
Prior/concomitant medication review	X	X	X	X	X	X	X	X	X	X	X	X	X
Adverse event (AE) monitoring	X	X	X	X	X	X	X	X	X	X	X	X	X
Physical examination											X		X
Height as measured by stadiometer											X		X
Tanner staging											X		X
Menstrual cyclicity (female subjects)	X	X	X	X	X	X	X	X	X	X	X	X	X
Vital signs ^b	X	X	X	X	X	X	X	X	X	X	X	X	X
Weight											X		X
Waist circumference measurement						X				X			X
Electrocardiogram (ECG)										X			
Hematology, chemistry, and urinalysis							X				X		
Hormonal Parameters ^c							X				X		
Serum prolactin							X				X		
Glycosylated hemoglobin (HbA _{1c})							X				X		
Glucose and lipid panel ^d							X				X		
Serum insulin and C-reactive protein							X				X		

Study Visit Number Study Visit Week (± 3 days)	V 1E	V 2E	V 3E	V 4E	V 5E	V 6E	V 7E	V 8E	V 9E	V 10E	V 11E	V 12E	V 13E
	Day 1	W2	W4	W6	W8	W12	W16	W20	W24	W28	W32	W36	W40
Urine drug screen			X		X	X	X	X	X	X	X	X	X
Urine β -hCG ^{e, f}			X		X	X	X	X	X	X	X	X	X
Simpson-Angus Scale (SAS)		X	X	X	X	X	X	X	X	X	X	X	X
Barnes Akathisia Rating Scale (BARS)		X	X	X	X	X	X	X	X	X	X	X	X
Abnormal Involuntary Movement Scale (AIMS)		X	X	X	X	X	X	X	X	X	X	X	X
Clinical Evaluations: SUBJECTS from D1050301 ONLY													
Children's Global Assessment Scale (CGAS)					X					X			X
Clinical Global Impression – Severity (CGI-S)		X	X	X	X	X	X	X	X	X	X	X	X
Pediatric Quality of Life Enjoyment and Satisfaction Questionnaire (PQ-LES-Q)					X					X			X
Udvalg for Kliniske Undersøgelser Side Effect Rating Scale (UKU)					X					X			X
Columbia Suicide Severity Rating Scale (C-SSRS)		X	X	X	X	X	X	X	X	X	X	X	X
Positive and Negative Syndrome Scale (PANSS)					X					X			X
CogState Computerized Cognitive Test Battery						X				X			
Clinical Evaluations: SUBJECTS from D1050325 ONLY													
Aberrant Behavior Checklist (ABC)					X					X			X
Clinical Global Impression – Severity (CGI-S)		X	X	X	X	X	X	X	X	X	X	X	X
Children's Yale-Brown Obsessive Compulsive Scales (CY-BOCS) modified for pervasive developmental disorders (PDDs)					X					X			X
Caregiver Strain Questionnaire (CGSQ)					X		X			X			X

Study Visit Number Study Visit Week (± 3 days)	V 1E	V 2E	V 3E	V 4E	V 5E	V 6E	V 7E	V 8E	V 9E	V 10E	V 11E	V 12E	V 13E
	Day 1	W2	W4	W6	W8	W12	W16	W20	W24	W28	W32	W36	W40
Clinical Evaluations: SUBJECTS from D1050326 ONLY	These clinical evaluations were to have been performed at Study Visit Number 9 in study D1050301 or D1050325 or at Study Visit Number 8 in study D1050326 and will serve as the baseline evaluations for this study.												
Children's Depression Rating Scale, Revised (CDRS-R)				X		X				X			X
Clinical Global Impression-Bipolar Version, Severity of Illness (CGI BP-S)		X	X	X	X	X	X	X	X	X	X	X	X
Children's Global Assessment Scale (CGAS)				X		X				X			X
Young Mania Rating Scale (YMRS)				X		X				X			X
Pediatric Quality of Life Enjoyment and Satisfaction Questionnaire (PQ-LES-Q)				X		X				X			X
Columbia Suicide Severity Rating Scale (C-SSRS)		X	X	X	X	X	X	X	X	X	X	X	X
Udvalg for Kliniske Undersøgelser Side Effect Rating Scale (UKU)		X		X		X				X			X
Pediatric Anxiety Rating Scale (PARS)				X		X				X			X
Attention-Deficit/Hyperactivity Disorder Rating Scale (ADHD-RS)				X		X				X			X
CogState Computerized Cognitive Test Battery						X				X			

Abbreviations: V = Visit; Wk = Week

^a Study drug will be dispensed only if a dose change is required.

^b Vital sign measurements to include orthostatic changes in blood pressure and heart rate.

^c Hormonal Parameters include the following measures: follicle stimulating hormone; luteinizing hormone; testosterone (male subjects only); estradiol (female subjects only).

^d Subjects will fast for laboratory tests.

^e Any positive urine β -hCG test will be confirmed by serum β -hCG.

^f Females subjects ≥ 11 years of age only.

If a subject discontinues from the study, all Visit 29E procedures will be performed at the discontinuation visit, within 48 hours of the last dose of study medication.

Table 4: Schedule of Assessments - Week 44 to 92

Study Visit Number Study Visit Week (± 3 days)	V 14E	V 15E	V 16E	V 17E	V 18E	V 19E	V 20E	V 21E	V 22E	V 23E	V 24E	V 25E	V 26E
	W44	W48	W52	W56	W60	W64	W68	W72	W76	W80	W84	W88	W92
Interactive Voice/Web Response System (IXRS) subject registry/visit	X	X	X	X	X	X	X	X	X	X	X	X	X
Dispense study medication	X	X	X	X	X	X	X	X	X	X	X	X	X
Study drug accountability/assess compliance	X	X	X	X	X	X	X	X	X	X	X	X	X
Clinical and Laboratory Evaluations: ALL SUBJECTS													
Prior/concomitant medication review	X	X	X	X	X	X	X	X	X	X	X	X	X
Adverse event monitoring	X	X	X	X	X	X	X	X	X	X	X	X	X
Physical examination			X						X				
Height as measured by stadiometer			X			X			X			X	
Tanner staging			X						X				
Menstrual cyclicity (female subjects)	X	X	X	X	X	X	X	X	X	X	X	X	X
Vital signs ^a	X	X	X	X	X	X	X	X	X	X	X	X	X
Weight			X			X			X			X	
Waist circumference measurement			X			X			X			X	
Electrocardiogram (ECG)			X						X				
Hematology, chemistry, and urinalysis			X						X				
Hormonal Parameters ^b			X						X				
Serum prolactin			X						X				
Glycosylated hemoglobin (HbA _{1c})			X						X				
Glucose and lipid panel ^c			X						X				
Serum insulin and C-reactive protein			X						X				
Urine drug screen	X	X	X	X	X	X	X	X	X	X	X	X	X
Urine β -hCG ^{d, e}	X	X	X	X	X	X	X	X	X	X	X	X	X

Study Visit Number Study Visit Week (± 3 days)	V 14E	V 15E	V 16E	V 17E	V 18E	V 19E	V 20E	V 21E	V 22E	V 23E	V 24E	V 25E	V 26E
	W44	W48	W52	W56	W60	W64	W68	W72	W76	W80	W84	W88	W92
Simpson-Angus Scale (SAS)	X	X	X	X	X	X	X	X	X	X	X	X	X
Barnes Akathisia Rating Scale (BARS)	X	X	X	X	X	X	X	X	X	X	X	X	X
Abnormal Involuntary Movement Scale (AIMS)	X	X	X	X	X	X	X	X	X	X	X	X	X
Clinical Evaluations: SUBJECTS from D1050301 ONLY													
Children's Global Assessment Scale (CGAS)			X			X			X			X	
Clinical Global Impression – Severity Scale (CGI-S)	X	X	X	X	X	X	X	X	X	X	X	X	X
Pediatric Quality of Life Enjoyment and Satisfaction Questionnaire (PQ-LES-Q)			X			X			X			X	
Udvalg for Kliniske Undersøgelser Side Effect Rating Scale (UKU)			X			X			X			X	
Columbia Suicide Severity Rating Scale (C-SSRS)	X	X	X	X	X	X	X	X	X	X	X	X	X
Positive and Negative Syndrome Scale (PANSS)			X			X			X			X	
CogState Computerized Cognitive Test Battery			X						X				
Clinical Evaluations: SUBJECTS from D1050325 ONLY													
Aberrant Behavior Checklist (ABC)			X			X			X			X	
Clinical Global Impression – Severity Scale (CGI-S)	X	X	X	X	X	X	X	X	X	X	X	X	X
Children's Yale-Brown Obsessive Compulsive Scales (CY-BOCS) modified for pervasive developmental disorders (PDDs)			X			X			X			X	
Caregiver Strain Questionnaire (CGSQ)			X			X			X			X	
Clinical Evaluations: SUBJECTS from D1050326 ONLY													

Study Visit Number Study Visit Week (± 3 days)	V 14E	V 15E	V 16E	V 17E	V 18E	V 19E	V 20E	V 21E	V 22E	V 23E	V 24E	V 25E	V 26E
	W44	W48	W52	W56	W60	W64	W68	W72	W76	W80	W84	W88	W92
Children's Depression Rating Scale, Revised (CDRS-R)			X			X			X			X	
Clinical Global Impression-Bipolar Version, Severity of Illness (CGI BP-S)	X	X	X	X	X	X	X	X	X	X	X	X	X
Children's Global Assessment Scale (CGAS)			X			X			X			X	
Young Mania Rating Scale (YMRS)			X			X			X			X	
Pediatric Quality of Life Enjoyment and Satisfaction Questionnaire (PQ-LES-Q)			X			X			X			X	
Columbia Suicide Severity Rating Scale (C-SSRS)	X	X	X	X	X	X	X	X	X	X	X	X	X
Udvalg for Kliniske Undersogelser Side Effect Rating Scale (UKU)			X			X			X			X	
Pediatric Anxiety Rating Scale (PARS)			X			X			X			X	
Attention-Deficit/Hyperactivity Disorder Rating Scale (ADHD-RS)			X			X			X			X	
CogState Computerized Cognitive Test Battery			X						X				

Abbreviations: V = Visit; Wk = Week

^a Vital sign measurements to include orthostatic changes in blood pressure and heart rate.

^b Hormonal Parameters include the following measures: follicle stimulating hormone; luteinizing hormone; testosterone (male subjects only); estradiol (female subjects only).

^c Subjects will fast for laboratory tests.

^d Any positive urine β -hCG test will be confirmed by serum β -hCG.

^e Females subjects ≥ 11 years of age only.

If a subject discontinues from the study, all Visit 29E procedures will be performed at the discontinuation visit, within 48 hours of the last dose of study medication.

Table 5: Schedule of Assessments - Week 96 to 105

Study Visit Number Study Visit Week (± 3 days)	V 27E	V 28E	EOS/ET V 29E ^a	F/U V 30E
	Wk96	Wk100	Wk104	Wk105
Interactive Voice/Web Response System (IXRS) subject registry/visit	X	X	X	X
Dispense study medication	X	X		
Study drug accountability/assess compliance	X	X	X	
Clinical and Laboratory Evaluations: ALL SUBJECTS				
Prior/concomitant medication review	X	X	X	X
Adverse event monitoring	X	X	X	X
Physical examination			X	
Height as measured by stadiometer			X	
Tanner staging			X	
Menstrual cyclicity (female subjects)	X	X	X	X
Vital signs ^b	X	X	X	X
Weight			X	
Waist circumference measurement			X	
Electrocardiogram (ECG)			X	
Hematology, chemistry, and urinalysis			X	
Hormonal Parameters ^c			X	
Serum prolactin			X	
Glycosylated hemoglobin (HbA _{1c})			X	
Glucose and lipid panel ^d			X	
Serum insulin and C-reactive protein			X	
Urine drug screen	X	X	X	
Urine β -hCG ^{e, f}	X	X	X	X

Study Visit Number Study Visit Week (± 3 days)	V 27E	V 28E	EOS/ET V 29E ^a	F/U V 30E
	Wk96	Wk100	Wk104	Wk105
Simpson-Angus Scale (SAS)	X	X	X	X
Barnes Akathisia Rating Scale (BARS)	X	X	X	X
Abnormal Involuntary Movement Scale (AIMS)	X	X	X	X
Clinical Evaluations: SUBJECTS from D1050301 ONLY				
Children's Global Assessment Scale (CGAS)			X	
Clinical Global Impression – Severity Scale (CGI-S)	X	X	X	
Pediatric Quality of Life Enjoyment and Satisfaction Questionnaire (PQ-LES-Q)			X	
Udvalg for Kliniske Undersøgelser Side Effect Rating Scale (UKU)			X	
Columbia Suicide Severity Rating Scale (C-SSRS)	X	X	X	X
Positive and Negative Syndrome Scale (PANSS)			X	
CogState Computerized Cognitive Test Battery			X	
Clinical Evaluations: SUBJECTS from D1050325 ONLY				
Aberrant Behavior Checklist (ABC)			X	
Clinical Global Impression – Severity Scale (CGI-S)	X	X	X	
Children's Yale-Brown Obsessive Compulsive Scales (CY-BOCS) modified for pervasive developmental disorders (PDDs)			X	
Caregiver Strain Questionnaire (CGSQ)			X	
Clinical Evaluations: SUBJECTS from D1050326 ONLY				
Children's Depression Rating Scale, Revised (CDRS-R)			X	
Clinical Global Impression-Bipolar Version, Severity of	X	X	X	

Study Visit Number Study Visit Week (± 3 days)	V 27E	V 28E	EOS/ET V 29E ^a	F/U V 30E
	Wk96	Wk100	Wk104	Wk105
Illness (CGI BP-S)				
Children's Global Assessment Scale (CGAS)			X	
Young Mania Rating Scale (YMRS)			X	
Pediatric Quality of Life Enjoyment and Satisfaction Questionnaire (PQ-LES-Q)			X	
Columbia Suicide Severity Rating Scale (C-SSRS)	X	X	X	X
Udvalg for Kliniske Undersøgelser Side Effect Rating Scale (UKU)			X	
Pediatric Anxiety Rating Scale (PARS)			X	
Attention-Deficit/Hyperactivity Disorder Rating Scale (ADHD-RS)			X	
CogState Computerized Cognitive Test Battery			X	

Abbreviations: V = Visit; Wk = Week; F/U = follow-up

^a If a subject discontinues from the study, all Visit 29E procedures will be performed at the discontinuation visit, within 48 hours of the last dose of study medication.

^b Vital sign measurements to include orthostatic changes in blood pressure and heart rate.

^c Hormonal Parameters include the following measures: follicle stimulating hormone; luteinizing hormone; testosterone (male subjects only); estradiol (female subjects only).

^d Subjects will fast for laboratory tests.

^e Any positive urine β -hCG test will be confirmed by serum β -hCG.

^f Females subjects ≥ 11 years of age only.

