#### **2.1.3. Visit Windows**

While the Time and Events Schedule of the protocol indicates the visit timing and procedures for each visit, the timing of a subject’s actual visit timing may not be exactly as per the protocol indicated target day/visit window (note that the protocol does not indicate required visit windows, but rather provides clear guidance for visit timing). Consequently, for the purpose of analysis, the conventions outlined below will be used to allocate the data collected at each actual visit to a planned protocol visit by defining analysis visit windows.

The reference day is study Day 1. Definition of baseline and endpoint is provided in [Sections 2.1.5 - 2.1.6](#).

If a subject has 2 or more visits (scheduled or unscheduled) in one analysis visit window, the visit closest to the target day will be used as the study visit for that analysis visit window. The other additional visit(s) in the same analysis visit window will not be included in the by-visit

descriptive summary analyses. However, measurements from this/these other additional visit(s) will be included in the subject listings and in the other safety analyses (eg, Potentially Markedly Abnormal Laboratory Values or the worst case analysis) to assure all on-treatment measurements are included. If 2 study visits occur the same number of days from the target day within the same visit window, the later one will be considered as the study visit for that target day.

Although all (scheduled and unscheduled) visits will be allocated to an analysis visit window, only planned protocol visits for each measurement will be included in the by-visit analyses. All tables and figures presenting data by visit will present only those timepoints where the applicable assessment was scheduled to be collected, unless otherwise noted below. Unscheduled and early termination data will be included for definition of endpoint or overall assessments. Data listings will present all data, regardless of visit.

Table 2 summarizes the analysis visit windows for all questionnaires, laboratory, weight, height, waist circumference, vital signs, ECG, cogstate, tanner stage, menstrual cyclicity, and other safety variables assessed at scheduled visits.

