## **Week 52 LOCF/Week 52 Endpoint**

In the event of missing data at Week 52 (per visit window in [Section 2.1.3](#)), the last post-OL baseline observation carried forward approach prior to Week 52 will be used to impute missing values.

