## **2.2. Methods of Analysis**

### **2.2.1. Statistical Hypotheses for Trial Objectives**

Because of the nature of an open-labeled study, no hypotheses are planned and to be tested.

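### One visit-window table for all assessments means a Week 52 lab, ECG, CogState, 12-weekly scale or growth value taken 14 or more days late is dropped by visit and replaced at Week 52 LOCF/Endpoint by an older one

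*Protocol*

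**What the plan says.** **Schedule.** Protocol "Table 4: Schedule of Assessments - Week 44 to 92" and the visit lists in Section 11.4 set three frequencies around Week 52:

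- Labs, ECG and CogState: Weeks 28, 52 and 76.
- PANSS, ABC, CDRS-R, YMRS, CGAS, PQ-LES-Q, UKU, PARS, ADHD-RS, CY-BOCS, CGSQ, weight, height and waist: Weeks 28, 40, 52, 64, 76 and 88.
- CGI-S, CGI-BP-S, SAS, BARS, AIMS, C-SSRS and vital signs: every 4 weeks, including Week 56.

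Nothing in the first two groups is scheduled at Week 56 or Week 60.

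**Windows.** The SAP does not follow these frequencies. Section 2.1.3 says "Table 2 summarizes the analysis visit windows for all questionnaires, laboratory, weight, height, waist circumference, vital signs, ECG, cogstate" and further safety variables. All share one row per study week: Week 52 is Days 351-378 and Week 56 is Days 379-406.

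**By-visit display.** The same section adds that "only planned protocol visits for each measurement will be included in the by-visit analyses", and that "All tables and figures presenting data by visit will present only those timepoints where the applicable assessment was scheduled to be collected".

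**Week 52 row.** SAP 2.1.6 defines Week 52 LOCF (effectiveness) and Week 52 Endpoint (safety) as the Week 52 value or, failing that, the last earlier post-baseline value. SAP 2.1.14.1 judges missingness by the window in 2.1.3 and states that "the last post-OL baseline observation carried forward approach prior to Week 52 will be used to impute missing values". SAP 2.1.11 puts a Week 52 row in the safety and effectiveness summaries.

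**The concern.** Analysis windows exist to keep off-schedule visits usable. For an assessment made every 4 weeks, Table 2 does that, because a late value moves to the next column and that column exists. For an assessment made every 12 or 24 weeks, the neighbouring window has no column. A Week 52 ECG or PANSS taken on Day 379 is assigned to Week 56 and disappears from the by-visit tables. Since the Week 52 window is then empty, and only earlier values may be carried forward, the Week 52 row reports a value from Week 40 or Week 28 although a measured one exists two weeks after target.

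At stake is the dating of the one-year result for growth, laboratory, ECG, cognitive and symptom measures in a study whose purpose is long-term safety and effectiveness.

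**Working it through.** **1. Reproduce the window.** Target day = 7 × week + 1, so Week 52 = 7 × 52 + 1 = Day 365. The neighbouring targets are Day 337 (Week 48) and Day 393 (Week 56). Midpoints are (337 + 365)/2 = 351 and (365 + 393)/2 = 379, and the midpoint day goes to the later window. This gives Days 351-378, or −14/+13 days, matching SAP Table 2.

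**2. Map deviations to windows.**

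| Deviation from Day 365 | Day | Window |
|---|---|---|
| 15 days early | 350 | Week 48 |
| 14 days early | 351 | Week 52 |
| 13 days late | 378 | Week 52 |
| 14 days late | 379 | Week 56 |
| 42 days late | 407 | Week 60 |
| 70 days late | 435 | Week 64 (scheduled for 12-weekly items) |

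**3. Find the value that replaces a late one** (target days from SAP Table 2, schedule from Protocol 11.4).

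| Assessment | At Week 56? | Last visit before Week 52 | Gap to Week 52 target |
|---|---|---|---|
| Labs, ECG, CogState | No | Week 28, Day 197 | (365 − 197)/7 = 24 weeks |
| 12-weekly scales, weight, height, waist | No | Week 40, Day 281 | (365 − 281)/7 = 12 weeks |
| CGI-S, CGI-BP-S, SAS, BARS, AIMS, C-SSRS, vital signs | Yes | Week 48, Day 337 | (365 − 337)/7 = 4 weeks |

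Against a dropped value on Day 379, the first two gaps are (379 − 197)/7 = 26 weeks and (379 − 281)/7 = 14 weeks. An unscheduled measurement in between would shorten them. Lab visits are taken from Section 11.4 and Appendix A Table 9 (Visits 6E and 10E), because the column alignment of Table 3 is unreliable in the text available. If the last earlier lab were at Week 32 (Day 225), its gap would be (365 − 225)/7 = 20 weeks.

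**4. Other cases.** A Week 52 assessment on Day 345 loses its by-visit column, but it is itself the last value before Week 52, so LOCF/Endpoint uses it. At Weeks 28 and 76 the final-analysis SAP has no carry-forward row, so an off-window value only reduces the by-visit N.

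**5. Possible size.** The documents report no distribution of visit days. Assume deviations are normal with mean 0. The share 14 or more days late is P(deviation > 13.5):

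- SD 5: 1 − Φ(2.70) = 0.35%, or 0.3% to one decimal
- SD 7: 1 − Φ(1.93) = 2.7%
- SD 10: 1 − Φ(1.35) = 8.9%

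These SDs put about 48%, 62% and 73% of visits outside ±3 days (|deviation| > 3.5). At SD 3 the late tail is about 0.0003%.

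**The case against.** The strongest reply is that the mechanism needs a serious deviation. The protocol allows ±3 days and the windows are 28 days wide, so few visits may be affected, and the SDs above are assumptions under which most or nearly half of visits breach the protocol. This stands as a limit on size, and it is why no count of subjects is given. It does not remove the defect: SAP 2.1.3 sets these windows precisely because actual visits may drift from target.

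Second, the data are not lost. Late values stay in listings, in the overall open-label worst-case analyses and, if last, in Endpoint. A reader might infer that safety signals are discarded; the SAP does not support that. What is lost is the value's place in the by-visit and Week 52 results. The first-52-week worst-case analyses do not recover it, since they stop at Day 365 (SAP 2.1.7).

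Third, the study is descriptive: "Because of the nature of an open-labeled study, no hypotheses are planned and to be tested". No test or error rate is affected. The Week 52 rows are still planned outputs and should use the measured one-year value where there is one.

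Fourth, lock 1 has taken place and the schizophrenia report is complete (SAP Section 1), so a new rule could leave two sets of results for D1050301 subjects. This is a real cost, dealt with in the fix.

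**Conclusion.** The point holds for assessments not made every 4 weeks. By the stated rules, a Week 52 value taken on Day 379 or later leaves the by-visit tables. It is replaced in the Week 52 row by one from 12 weeks before target (12-weekly scales, growth) or 24 weeks before target (labs, ECG, CogState), unless an unscheduled measurement lies closer. The thresholds and gaps follow exactly from the documents. The frequency does not: 0.3%, 2.7% or 8.9% rests wholly on the assumed SDs and a normal distribution centred on target.

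Four stronger readings are tempting but not supported:

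- **That one-year change is understated.** An older value understates change only if the measure moves steadily away from baseline. Height in growing children fits that; for most measures nothing in the documents establishes it. The safe word is misdated.
- **That early visits suffer the same replacement.** They lose only the by-visit column, so both tails should not be counted for the Week 52 row.
- **That Weeks 28 and 76 are equally affected.** Only the by-visit column is lost there.
- **That all ratings are affected.** The 4-weekly ratings have a Week 56 column. Their Week 52 carry-forward is 4 weeks before target, though a late value can still lose its place to a Week 56 visit nearer Day 393.

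This is a cheap and worthwhile improvement to the SAP, not a threat to the study's overall safety conclusions.

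**What to change.** In SAP 2.1.3, keep Table 2 for 4-weekly assessments and add a rule for sparser ones:

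- A value falling in a window where that assessment is not scheduled is assigned to the nearest visit at which it is scheduled, provided that visit has no value of its own and lies within 42 days. Ties go to the later visit.
- For 12-weekly items the bounds are the midpoints (281 + 365)/2 = 323 and (365 + 449)/2 = 407, so Week 52 takes Days 323-406. For labs, ECG and CogState, the 42-day limit alone would also admit Day 407; fix one bound for all.
- State whether early-termination values qualify.
- Derive Week 52 LOCF/Endpoint after this step.

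Apply the rule in the full report after lock 2. For D1050301 subjects, already reported from lock 1, show it as a sensitivity table. Report how many values are reassigned, which also supplies the missing frequency.

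The cost is one SAP paragraph and a small programming change, with no new data. The downsides are that a few values labelled Week 52 may lie up to 6 weeks from target, still closer than the 12 or 24 weeks of those they replace, and that D1050301 results may differ slightly from the lock 1 report.

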8. SELECTION AND WITHDRAWAL OF SUBJECTS

The following inclusion/exclusion criteria must be met prior to enrolling the subject into the study.

